1. SUMMARY

1.0. Type of application:

Open-label, phase III, prospective, multicenter study.

1.1. Identification of the developer:

Fundació Clínic per a la Recerca Biomèdica
Manager: [name] [name]
[name]
[name]

1.2. Title of the clinical trial:

Phase III open-label study to evaluate the efficacy and safety of boceprevir treatment in patients co-infected with HIV and HCV (genotype 1), who have failed prior treatment with peginterferon and ribavirin.

Version / Date: 1.0, dated 18 September 2012.

1.3. Protocol code: BOC-HIV

EudraCT number: 2012-003984-23

1.4. Principal Investigator and Study Coordinator: [name] [name]

Collaborating researchers: [name] [name].

1.5. Centres in which the trial is planned to be carried out:

The centres where the trial is planned to be carried out are detailed in the document "*List of participating centres and researchers*".

1.6. Clinical Research Ethics Committees that have approved the trial:

The trial has been presented to all the CEICs corresponding to the participating centers, and the CEIC of the Hospital Clínic de Barcelona has also been assigned as a reference CEIC.

1.7. Name and qualification of the person responsible for monitoring:

[name].
Clinical Trials Unit.
CTU Clinic. Clinical Pharmacology Service.
(Hospital Clínic de Barcelona).
Head of the CTU: [name] [name]

1.8. Study drug information:

Boceprevir: The drug has final approval by the Ministry of Health. As stated in its technical sheet (see annexes).

1.9. Phase of the clinical trial: Phase III.

1.10. Objectives:

1.10.1. Main objective:

The primary objective of this study is to evaluate the safety and efficacy of response-guided therapy with boceprevir 800 mg three times daily orally (o.v.) in combination with peginterferon (alpha-2b or alpha-2a) and ribavirin in genotype 1 HIV- and HCV-infected patients in whom prior HCV treatment with ribavirin-associated pegylated interferon had failed.

1.10.2. Secondary objectives:

- To define predictors of sustained virologic response (SVR), such as epidemiological factors, disease characteristics, clinical status of HIV infection, and response during treatment, especially at weeks 4, 8, 12, and at the end of treatment.
- To determine the percentage of patients with undetectable HCV RNA at treatment weeks (ST) 4, 8, and 12 and at the end of treatment.
- Evaluate virologic response based on baseline characteristics
- To investigate HCV resistance following virological failure with a regimen containing boceprevir (BOC). Blood samples should be obtained at baseline, at the time of virological failure (VF) (VF: two consecutive samples with signs of HCV replication after HCV was undetectable – below the lower limit of detection – or HCV RNA rebound equal to or greater than one logarithmic unit with respect to the RNA nadir) and six months after virological failure. The evaluation of resistance will be carried out in a single center (coordinating center: Hospital Clínic, Barcelona) by means of population sequencing of the genome that encodes the HCV protease.

1.11. Design:

Open-label, Phase III, prospective, multicenter study.

1.12. Disease under study:

HCV (hepatitis C virus) co-infection (genotype 1 (subtype a or b)) + HIV (acquired immunodeficiency virus)

1.13. Assessment variables:

1.13.1. Main

- **Primary efficacy endpoint:** achievement of SVR (sustained virologic response, defined as an undetectable plasma HCV RNA at follow-up week (SS) 24. If SS24 data are not available in a patient and the HCV RNA in SS12 is undetectable, SVR will be considered to be present.

1.13.2. Secondary

- Percentage of patients with virologic response (HCV RNA undetectable at weeks 4, 8, or 12) in those who achieve SVR.
- Percentage of patients with HCV RNA undetectable in SS12.
- Percentage of patients with undetectable HCV RNA 72 weeks after randomization.
- To investigate the resistances that appear after virological failure. Blood samples will be obtained at baseline, at the time of virological failure (VF) (VF defined as two consecutive samples with detectable HCV-RNA after the HCV-RNA is undetectable – below the lower limit of detection – or HCV-RNA rebound equal to or greater than one logarithmic unit with respect to the RNA nadir) and six months after virological failure. The evaluation of resistance will be carried out in a single center (coordinating center: Hospital Clínic, Barcelona) by means of population sequencing of the genome encoding the HCV protease
- Safety

1.14. Study population and total number of patients:

Adult patients with well-controlled chronic HIV infection and chronic hepatitis with genotype 1 C virus (subtype a or b), who have failed previous treatment with pegylated interferon associated with ribavirin.

A total of 128 patients will be included.

1.15. Duration of treatment:

The approximate expected duration for the inclusion of patients is 12 months, and the duration of treatment and follow-up of the included patients will be extended by a maximum of 72 weeks.

1.16. Schedule and expected completion date:

The study is expected to begin, once the permits have been obtained, in March 2013. The recruitment period will be 12 months. Patients will be followed for 6 months after the end of treatment. The study is expected to be completed in November 2015.

3.1 Identification of the test

Title:

Phase III open-label study to evaluate the efficacy and safety of boceprevir treatment in patients co-infected with HIV and HCV (genotype 1) who have failed prior treatment with peginterferon and ribavirin.

Open-label, Phase III, prospective, multicenter study.

Version / Date: 1.0 (18-09-2012)

EudraCT number: 2012-003984-23

3.7 Information on the laboratories or technical departments involved

Daily clinical evaluation of patients enrolled in the study, routine blood/urine laboratory determinations, and viral determinations (HCV and HIV), will be performed in the corresponding services at each center participating in the study.

Determinations of HCV mutations that confer resistance to boceprevir in patients with virological failure will be carried out centrally in the Microbiology Laboratory of the Hospital Clínic de Barcelona.

3.8 Monitoring

CTU (clinical Trial Unit).

Responsible for monitoring:

[name]. [contact]

[contact] [name] [contact]

Head of the CTU:

[name] [name].

Clinical Pharmacology Service.

Hospital Clínic de Barcelona

4. Justification

Currently, the standard of care for chronic hepatitis C virus (HCV) in patients with concurrent HIV and HCV infection is peginterferon plus ribavirin for 48 weeks. Although the sustained virologic response rate (SVR) has improved markedly in recent years, in most studies it remains below 50%-55%.

As a result, more than 50% of patients who fail treatment have no treatment options and will develop progressive liver fibrosis. In fact, end-stage liver disease is the main cause of morbidity and mortality in patients co-infected with HIV and HCV, and its incidence is higher in patients without SVR to treatment with peginterferon plus ribavirin.

New approaches are needed to try to improve response in these patients. Recently, excellent results have been presented with a triple therapy based on peginterferon, ribavirin and the new HCV protease inhibitors telaprevir and boceprevir in patients with HCV monoinfection.

Although triple therapy achieves a higher rate of SVR, it is also true that the use of three drugs can be more toxic and will be more expensive. Preliminary data suggest that response-guided therapy (TGR) (32 weeks of triple therapy) in patients with HCV monoinfection can achieve the same virological outcomes as standard triple therapy (44 weeks) but with lower toxicity and lower cost. This point will be investigated in the present study.

Of the patients in whom previous treatment with peginterferon plus ribavirin has failed, the most difficult subgroup to rescue is those with no viral response. There are currently doubts about what the response to triple therapy will be in patients with a zero viral response to dual therapy and whether 44 weeks of treatment will be necessary in this subgroup of patients or whether the TGR approach can be applied. Information on this field is not available in patients with co-infection with HCV and HIV, and we believe that our study can provide valuable information on this important topic.

Results from a phase II, double-blind, comparative study of boceprevir and placebo in patients with controlled HIV co-infection who had not received HCV treatment have recently been published.

Efficacy and safety results were similar to those previously described in patients with HCV monoinfection. The overall sustained viral response was 61% in patients treated with boceprevir, compared with no more than 39% in those treated with peginterferon/ribavirin. Although the efficacy data are encouraging, response-guided therapy has not been formally investigated.

Several studies are underway to evaluate the efficacy and safety of HCV protease inhibitor triple therapy in HIV-HCV co-infected patients previously treated with peginterferon and ribavirin, but response-guided therapy has not been evaluated so far. The main hypothesis of this proposal is that response-guided triple therapy with boceprevir could obtain better SVR than classic treatment with peginterferon plus ribavirin.

4.1 Identification of the investigational medicinal product

Generic name: Boceprevir

Trade name: Victrelis®

Composition: boceprevir 200 mg.

Pharmaceutical form: hard gelatin capsules.

Generic name: Peginterferon (alpha-2b or alpha-2a)

Trade name: Pegintron® or Pegasys®

Composition: peginterferon alfa-2b 80-150mcg or peginterferon alfa-2a: 180 micrograms

Pharmaceutical form: solution for injection

Generic name: Ribavirin Trade name:

Ribavirin Teva®.

Composition: ribavirin: 200 mg

Dosage form: hard capsule

4.2 Investigational Drug Information

Boceprevir: The drug has final approval by the Ministry of Health. Date of first authorisation 18/07/2011.

4.3 Treatment Regimen

PEG-IFN alfa-2a or 2b and ribavirin will be provided by each hospital and will be administered in accordance with the approved technical data sheets.

BOC (Boceprevir). Provided by the study sponsor.

Description:

BOC is supplied in 200 mg capsules. Each capsule contains 200 mg of BOC, sodium lauryl sulfate, microcrystalline cellulose, lactose monohydrate, croscarmellose sodium, pregelatinized starch, and magnesium stearate packaged in number 0 hard gelatin capsules. Each capsule contains approximately 56 mg of lactose monohydrate. In people with lactase deficiency, the clinical manifestations of lactose intolerance require 3 to 5 g of lactose (4 to 7 times the total amount of BOC capsules) to appear.

Route of administration: oral

Dosage: total daily 2400 mg, (12 capsules).

Storage: keep in the fridge at a temperature between 2°C and 8°C. The products of the study must be stored in a safe place with limited access and in the storage conditions specified on the supply label.

[figure not shown]
Dosage Schedule:

Boceprevir is administered three times a day using a dosing schedule of 4 capsules every 8 hours. Actual times of dose administration may be modified to fit the patient's schedule, although 7- to 9-hour

intervals between administrations should be maintained. All doses of boceprevir will be given with food (a small snack is sufficient).

Study period and treatment:

All patients will receive an initial 4 weeks of bitherapy with Peg-Interferon and ribavirin (PR).
-If there is a decrease in HCV RNA greater than 1 logarithm with respect to baseline HCV-RNA, the patient will be included in the treatment scheme detailed below.

-If the RNA drop is ≤ 1 log at week 4, PR/boceprevir will be administered for an additional 44 weeks. All cirrhotic patients will receive PR for 4 weeks, followed by RP/boceprevir for another 44 weeks

4.4 Compliance Statement

The study will be carried out in accordance with the principles emanating from the Declaration of Helsinki, and according to the legal regulations in force (Royal Decree 223/2004), and will not begin until the approval of the reference CEIC and the approval of the AEMPS have been obtained.

Patients will be informed orally and in writing and all relevant information tailored to their level of understanding will be communicated to participants.

(See Attachment III: Patient Information Sheet and Attachment III: Written Consent Sheet.)
The patient will be informed that their participation in the study will be treated with the same confidentiality as their clinical documentation and that only the people involved in the study will have access to their data. The patient's name will not appear in any publication or communication of the results of the study.

4.5 Study population

Adults with controlled HIV-1 infection and chronic HCV hepatitis genotype 1 (subtype a or b) who did not achieve SVR with prior treatment with any peginterferon alfa plus ribavirin.


5. Objective and Purpose of the Trial

Main:

The primary objective of this study is to evaluate the safety and efficacy of response-guided therapy with boceprevir 800 mg three times daily orally (o.v.) in combination with peginterferon (alpha-2b or alpha-2a) and ribavirin in genotype 1 HIV- and HCV-infected patients in whom prior HCV treatment with ribavirin-associated pegylated interferon had failed.

Side:

- To define predictors of sustained virologic response (SVR), such as epidemiological factors, disease characteristics, clinical status of HIV infection, and response during treatment, especially at weeks 4, 8, 12, and at the end of treatment.
- To determine the percentage of patients with undetectable HCV RNA at treatment weeks (ST) 4, 8, and 12 and at the end of treatment.
- To evaluate the virological response according to baseline characteristics.
- To investigate HCV resistance after virological failure with a boceprevir-containing regimen (BOC). Blood samples should be obtained at baseline, at the time of virological failure (VF) (VF: two consecutive samples with signs of HCV replication after HCV was undetectable – below the lower limit of detection – or HCV RNA rebound equal to or greater than one logarithmic unit with respect to the RNA nadir) and six months after virological failure. The evaluation of resistance will be carried out in a single center (coordinating center: Hospital Clínic, Barcelona) by means of population sequencing of the genome that encodes the HCV protease.

6. Trial Design

Open-label, Phase III, prospective, multicenter study.

6.1 Main and secondary variables:

Primary endpoint:

The primary efficacy endpoint is the achievement of SVR, defined as an undetectable plasma HCV RNA at follow-up week (SS) 24.

If SS24 data are not available in a patient and the HCV RNA in SS12 is undetectable, SVR will be considered to be present.

Rules of futility:

HCV treatment failure is defined as follows:

- HCV RNA in serum >100 IU/mL at week 12
 - Or
 - Confirmed increase in serum HCV RNA to >1,000 IU/mL at any time after week 12
 - Or
 - detectable HCV RNA (above the lower limit of detection of HCV assay COBAS® Taqman® v2.0. de Roche) in week 24

Secondary endpoints:

- Percentage of patients with virologic response (HCV RNA undetectable at weeks 4, 8, or 12) in those who achieve SVR.
- Percentage of patients with HCV RNA undetectable in SS12.
- Percentage of patients with undetectable HCV RNA 72 weeks after randomization.
- HCV resistance after treatment with BOC-containing therapy. Blood samples will be obtained at baseline and after HCV virological failure, and at the end of the study a resistance analysis will be performed in a single center (Hospital Clínic, Barcelona).
- Safety.

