6.6 Termination and/or Discontinuation Criteria

The treatment will be **compulsorily** terminated during the study for any of the following reasons:

- Patient with HCV RNA >100 IU/mL in ST12 or detectable HCV RNA in ST24.
- Suicide or homicide thoughts or attempts.
- Severe depression or major depressive episode.
- Positive test result for non-prescription opioids, methamphetamines, or cocaine.
- Pregnancy during the study.
- Virological rebound, defined as:

Any patient who obtains an undetectable HCV RNA and subsequently presents an HCV RNA > 1,000 IU/ml.

Once virologic rebound has been identified, genotypic resistance will be characterized by HCV RNA sequencing in suitable samples, such as those collected at the time of rebound and during the follow-up period.

Treatment **may** be terminated during the study for any of the following reasons:

- The medical investigator determines that a SAE is possibly or likely related to the study drug.
- Failure to administer, evaluate, or other study requirements.

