8.1 Treatment branches

An open-label, single-arm, multicenter study to evaluate the safety and efficacy of a regimen with boceprevir in polytherapy with peginterferon alfa-2b 1.5 µg/kg or peginterferon alfa-2a 180 µg/kg once weekly subcutaneously (s.c.) and oral ribavirin in adult patients with controlled HIV coinfection in whom prior treatment of chronic hepatitis C with peginterferon and ribavirin has failed.

Since early response to peginterferon (PEG-IFN) and ribavirin (RVB) at week 4 is predictive of response to treatment, either SVR or null response (high negative predictive value: 96%), the duration of response-guided treatment with BOC will depend on the response in ST4, ST8, and ST12.

Patients who achieve a reduction in HCV RNA viral load greater than or equal to one logarithmic unit at week 4 (after the bitherapy phase) will then undergo triple therapy for 32 weeks. If HCV RNA is undetectable at week 8, they will end the tto after 32 weeks of triple therapy and will be followed for another 24 weeks. If HCV RNA is detectable at week 8, at the end of the 32 weeks of triple therapy, patients will receive dual therapy with pegylated interferon and ribavirin for an additional 12 weeks and then follow up for 24 weeks.

Patients who do not achieve a decrease in HCV RNA viral load greater than one logarithmic unit at week 4 after the initial phase of bitherapy (or those who have grade 4 fibrosis - cirrhosis) will receive triple therapy for 44 weeks and will be followed for an additional 24 weeks.

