11.2 Sample size

The primary objective of this study is to estimate SVR with response-guided therapy with boceprevir in patients with controlled HIV infection and chronic hepatitis C with genotype 1 virus in whom prior treatment with peginterferon/ribavirin has failed.

Since no comparative analysis is to be performed, the sample size depends on the accuracy of the SVR calculation. SVR from double treatment with peginterferon and ribavirin ranges from 27% to 39%.

The expected SVR with boceprevir triple therapy is 60%. If we define a margin of error ($60\% \pm 8.5\%$) that encompasses the maximum SVR observed with dual therapy (39%), the required sample size based on a bilateral 95% confidence interval is 128 patients.

The sample size calculation for the different RVM values was based on a bilateral 95% confidence interval for different levels of accuracy.

Stratification

Since this is a non-randomized study, no stratification is planned; however, for the purposes of data analysis, patients will be classified according to the type of failure of previous HCV treatment (no response, virologic rebound, and relapse).

No response: HCV RNA positivity at week 12.

1. Partial response. Patients who achieved at least a reduction in HCV RNA of two logarithmic units from baseline at week 12 but still had viremia at the end of treatment.
2. Null response. Patients who did not achieve a reduction of two logarithmic units of HCV RNA at week 12.

Rebound: negativity for HCV RNA at week 12, but positivity before week 48.

Relapse: HCV RNA undetectable at the end of treatment and subsequently detectable during 24 weeks of follow-up.

As this is an exploratory study, the inclusion of difficult-to-treat patients, such as those with no response (reduction in HCV RNA of less than two log units with prior HCV treatment) or with cirrhosis, will be limited to 30% of the study population.

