11.3 Analysis

In this open study, all variables will be tabulated. Quantitative variables will be described by the number of available and omitted observations, the mean, the median, the standard deviation, the interval (minimum and maximum) and the first and third quartiles. Of the qualitative variables, the frequency and percentage will be presented. Omitted values will be tabulated with their frequency, but will not be included in the calculation of the percentages.

The primary endpoint will be assessed with a bilateral CI of 95% around the observed proportion of SVR. The analysis of the primary endpoint in SVR will be carried out in two ways. Patients who withdrew from the study within the first four weeks will be included in the main analysis, which will be counted as SVR failures. As a secondary analysis, an SVR analysis will also be performed, but restricted to patients who have not withdrawn from the study in the bitherapy period in the first four weeks. In both analyses, patients in whom SVR data are lacking due to premature withdrawal from the study at any time after the initial bitherapy period of the first four weeks will be included and counted as SVR failures.

Inferential analysis of boceprevir efficacy will be assessed by SVR at week 24 and the 95% confidence interval. A similar analysis will be applied to evaluate the secondary variables. For continuous quantitative variables, the mean or median and the 95% confidence interval or the interquartile interval shall be calculated.

Descriptive analyses of treatment-occurring adverse events and treatment-occurring adverse events that are possibly or likely related to the study drug will be performed. With regard to the safety assessment in the AEs, the 95% CI of the percentage of grade 3 or higher adverse events and other serious adverse events reported by the centres shall be provided. The highest grade episode per person over time will be used. Descriptive tables will be provided summarizing the events and the number of people who have presented the events by grade.

Variations in HIV-1 viral load or RNA and CD4+ T cell count at each post-enrollment visit will be summarized. The rates and reasons for premature discontinuation of treatment, including HCV treatment failures, will be summarized.

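### The week-72 secondary endpoint is a planned time point only for patients who complete a 48-week course, and section 6.1 puts early response on a different denominator from section 5

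*Combined protocol and SAP*

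**What the plan says.** **Week 72.** The secondary endpoints in 1.13.2 and 6.1 include "Percentage of patients with undetectable HCV RNA 72 weeks after randomization". Section 8.1 describes a single arm, and 11.2 states: "Since this is a non-randomized study, no stratification is planned".

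Treatment length depends on response. After a 4-week lead-in (4.3), patients with an adequate week-4 fall and undetectable HCV RNA at week 8 take the short course. Section 8.1 says of them that "they will end the tto after 32 weeks of triple therapy and will be followed for another 24 weeks". The other two paths in 8.1 last 48 weeks in total, also with 24 weeks of follow-up. Section 6.6 makes stopping compulsory for a "Patient with HCV RNA >100 IU/mL in ST12 or detectable HCV RNA in ST24". Section 1.16 adds: "Patients will be followed for 6 months after the end of treatment".

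**Missing values.** Section 11.3 says: "Omitted values will be tabulated with their frequency, but will not be included in the calculation of the percentages". Section 11.5 rules out imputation and confines analysis to available data. For SVR, 11.3 counts as failures "patients in whom SVR data are lacking due to premature withdrawal from the study at any time after the initial bitherapy period", and it also says: "A similar analysis will be applied to evaluate the secondary variables".

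**Early response.** Sections 1.10.2 and 5 ask for the percentage of patients with undetectable HCV RNA at treatment weeks 4, 8 and 12 and at end of treatment. Sections 1.13.2 and 6.1 give the percentage only among patients who reach SVR, and leave out end of treatment. Section 11.3 lists virologic response at weeks 4, 8, 12 and 24 with no SVR condition.

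**The concern.** A fixed calendar endpoint does not suit a trial in which treatment length, and so the end of follow-up, varies by design. Patients whose treatment was shortened because they responded well would have no planned week-72 value, and neither would patients stopped early for poor response. A reader of the results would take a percentage of patients to mean the whole trial population. The short course matters most here, because section 4 presents response-guided duration as a question the study will investigate.

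The early-response item raises a smaller problem. The proportion of SVR patients who responded early is not the same quantity as the proportion of patients who responded early. The plan could report either one under a similar label.

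**Working it through.** **The plan's own figure.** Section 11.2 gives an expected SVR of 60%, a margin of 8.5 points and a two-sided 95% interval. n = 1.96² × 0.60 × 0.40 / 0.085² = 127.6, rounded up to 128. This reproduces, and nothing below changes it.

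**Last planned follow-up, counted from Day 1.** The inputs are the lead-in in 4.3, the paths in 8.1, the stopping rule in 6.6 and the follow-up period in 1.16.

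| Path | Sum (weeks) | Last planned follow-up | Week 72 planned? |
|---|---|---|---|
| Short course | 4 + 32 + 24 | week 60 | no, 12 weeks later |
| Detectable at week 8 | 4 + 32 + 12 + 24 | week 72 | yes |
| 44 weeks of triple therapy | 4 + 44 + 24 | week 72 | yes |
| Stopped at ST12 | 12 + 24 | about week 36 | no, about 36 weeks later |
| Stopped at ST24 | 24 + 24 | about week 48 | no, about 24 weeks later |

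Section 6.5 agrees: it gives 72 weeks as a maximum for treatment plus follow-up, not as a visit common to all patients. For patients who complete 48 weeks, 48 + 24 = 72, so week 72 is SS24. The one difference is that the primary endpoint lets an undetectable SS12 value stand in for a missing SS24.

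**How many patients have a planned value.** The documents do not give the short-course share s. Assume 20% to 50%. The number is then at most 128 × (1 − s): 102 at s = 20% and 64 at s = 50%, and fewer once early-stopped patients are removed. At 60%, the 95% half-width 1.96 × √(0.24/n) is 8.5 points for n = 128, 9.5 for n = 102 and 12.0 for n = 64.

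**Direction.** Available-data analysis drops two kinds of patient. Section 8.1 treats early response as predictive of outcome, so short-course patients are likely to do better than average. Patients stopped at ST12 or ST24 are treatment failures under 6.1. Dropping the first group would tend to lower the figure, and dropping the second would raise it. The documents give neither share, so the net effect cannot be signed.

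**Early response.** At the planned 60%, SVR patients number 0.60 × 128 = 76.8, about 77. The 6.1 denominator is therefore about 77, against 128 for all patients, and leaves out about 51. Comparing the lists:
- Weeks 4, 8 and 12 among all patients: asked for in section 5, covered by 11.3, not by 6.1.
- End of treatment: asked for in section 5, absent from the 6.1 endpoints and the 11.3 lists.
- SVR by week-12 status: week 12 is named in the first secondary objective, but the 11.3 subgroups give only week 4 and week 8.

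**The case against.** **The anchor.** The word randomization may be leftover wording; it also appears in exclusion criterion 9. The visit tables start at Day 1, and 4 + 44 + 24 = 72 fits the stated maximum. A reader might infer that the endpoint has no usable time zero. That goes too far: Day 1 is evident and only needs stating. Stating it does not help the short-course patient, whose follow-up still ends at week 60.

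**The visit tables.** A reader might infer from the printed tables that no HCV RNA is measured after ST 48/dFT. Those tables are headed as treatment schedules, and the primary endpoint itself presupposes SS12 and SS24 samples. Their end point proves little, and the argument does not need it.

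**Scoring.** A reader might infer that cured short-course patients would be counted as failures, giving a large downward bias. The failure rule in 11.3 is limited to premature withdrawal, and a patient who completes the short course has not withdrawn. The instruction to treat secondary variables similarly leaves some ambiguity, but no passage makes planned completers failures. The more direct reading is that they drop out of the percentage.

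**The resistance sample.** The sample six months after virological failure could fall near week 72 in a late failure. It exists only for failures, so it cannot supply a value for a cured short-course patient.

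**Early response.** A reader might infer that the section 5 objective goes unanalysed, or that a 6.1 figure says almost nothing about all patients. Section 11.3 lists the unrestricted weekly responses and says all variables will be tabulated. The range of all-patient values compatible with one 6.1 figure is only a logical bound, and its extremes sit badly with the predictive claim in 8.1. The SVR-only figure can serve the predictor objective, and the regression in 11.3 could take in week 12. What stands is the differing denominator and the unlisted items.

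**Conclusion.** The point holds and is minor. Week 72 lies within planned follow-up only for patients who complete a 48-week course, and there it repeats SS24. Under the available-data rules the result would describe that group under a label that promises all patients. This follows from the durations in 4.3, 6.6, 8.1 and 1.16, with Day 1 taken as time zero. The counts of 102 and 64 rest on an assumed short-course share of 20% to 50%. No direction or size of bias is claimed.

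The early-response mismatch is real but smaller. What remains is an SVR-only denominator in 1.13.2 and 6.1, no listed end-of-treatment response, and no listed SVR by week-12 status. These are descriptive secondary analyses; the primary endpoint and N = 128 stand.

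**What to change.** **Week 72.** Delete the endpoint from 1.13.2 and 6.1, since SS24 already covers it. Alternatively, restrict it to patients on a 48-week course, count from Day 1, and label it as the SS24 time point.

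**Early response.** In 1.13.2 and 6.1, define it as the percentage of all patients in the main SVR analysis with undetectable HCV RNA at weeks 4, 8 and 12 and at each patient's own end of treatment. Count patients who withdrew from the study before the time point as not undetectable. Assess patients stopped by protocol for end-of-treatment response at their own stop. The share among SVR patients can stay as an added description, labelled as such. Add end-of-treatment response and SVR by week-12 status to the lists in 11.3.

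**Cost.** Wording changes in three sections and slightly more tabulation. No new samples are needed if ST 48/dFT serves as each patient's own end-of-treatment visit. The text should confirm this, because section 17 prints no HCV RNA sample at ST 36, where the short course ends (4 + 32).
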